Nasal swab kit and insulated cooler bag training and distribution						To be distributed before the start of the influenza season				
Participant diary review by qualified site staff ^{c,o}			●			●				
Blood Draw Volumesⁱ:										
Participants in the main study										
Approximate daily blood draw, mL	7.5	41.5	17.5	30	15	17.5	30	30	30	32.5
Approximate cumulative study blood draw, mL	7.5	49	66.5	96.5	111.5	129	159	189	219	–

^a 1 pre-dose; ^b pre- and post-dose; ^c blood samples for immunogenicity will only be taken if the early exit is at least 14 days after the previous immunogenicity blood draw; ^d if within 7 days of the last vaccination; ^e if within 28 days of the last vaccination

- For those participants who are unable to continue participation in the study up to Day 365±30 days, but for whom consent is not withdrawn, an exit visit will be conducted as soon as possible.
- An additional telephone call will be made to sentinel participants 48 hours post-vaccination to collect safety information. A phone call or other means of communication should be made to all participants 3 to 5 days after Day 1 and Day 57 visits to ensure that participants are completing the diary without issues.
- It is important to calculate visit window for Day 8, Day 29, Day 64, Day 85 and Day 238 visits with respect to the last vaccination visit. For example, Day 64 should be calculated with respect to vaccination 2 = VAC 2 + 7 days (+ 2 days window), and not as 64 days (+ 2 days window) after vaccination 1. If any of the participants for the 7-day post-dose safety review come in earlier than Day 8 for Visit 3 or Day 64 for Visit 6 (which will be a protocol deviation), a subsequent phone call will be made at the end of the diary period to collect diary card information recorded between the actual visit and the end of the 7-day post-dose diary period on Day 8 and Day 64, respectively.
- Signing of the ICF should be done before any study-related activity.
- A full physical examination, including height and body weight, will be carried out at screening. At other visits, an abbreviated, symptom-directed examination will be performed if determined necessary by the investigator. A symptom-directed physical examination may be repeated if deemed necessary by the investigator.
- Supine systolic and diastolic blood pressure, heart rate and respiratory rate after at least 5 minutes rest. It is recommended that vital signs are measured before blood draws.

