- To include inclusion criteria [4](#), [6](#) and [8](#), and exclusion criteria [2](#), [8](#), [9](#), [10](#), [13](#), [14](#), and [21](#).
- Investigator must check for acute illness or body temperature $\geq 38.0^{\circ}\text{C}$ (100.4°F) at the time of vaccination. In such cases, the participant may be vaccinated up to, and no later than 10 days after the scheduled vaccination, or be withdrawn at the discretion of the investigator.
- Blood sample volumes are approximate. Refer to the central laboratory manual or requirements of local laboratories for additional details. Additional blood samples may be collected for safety assessment and participants with influenza-like illness (Section [1.3.2](#), Schedule of Activities – Assessments for Participants With Influenza-like Illness [ILI]).
- Participants will be closely observed for a minimum of 30 minutes post-vaccination. Any unsolicited, solicited injection site and systemic AEs, and vital signs (supine systolic and diastolic blood pressure, heart rate, respiratory rate and body temperature) will be documented by study-site personnel following this observation period.
- All AEs and special reporting situations, whether serious or non-serious, that are related to study procedures or that are related to non-investigational (concomitant) sponsor products will be reported from the time a signed and dated ICF is obtained onwards. All SAEs and AEs leading to discontinuation from further study vaccination, will be reported from the day of first vaccination onwards until the end of the study.

1. Concomitant therapies will be collected from the signing of the ICF until 28 days after the first vaccination and from the second vaccination through the following 28 days, and additionally outside of these periods when associated with an SAE.

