2.3.3 Benefit-Risk Assessment Related to Study Vaccination

Based on the available data and proposed safety measures, the overall benefit-risk assessment for this clinical study is considered acceptable for the following reasons:

- Only participants who meet all inclusion criteria and none of the exclusion criteria (specified in Section 5, Study Population) will be allowed to participate in this study. The eligibility criteria include adequate provisions to minimize the risk and protect the well-being of participants in the study.
- Safety will be closely monitored throughout the study:
 - In general, safety evaluations will be performed at scheduled visits during the study, as described in Section 1.3, Schedule of Activities.

- After each vaccination, participants will remain at the study site for at least 30 minutes and will be closely observed by site staff. Necessary emergency equipment and medications must be available in the clinic to treat severe allergic reactions. Participants will use a diary to document solicited signs and symptoms. Details are provided in Section 8.2, Safety Assessments and Section 8.3, Adverse Events, Serious Adverse Events, and Other Safety Reporting.
 - The investigator or the designee will document unsolicited adverse events (AEs) as indicated in Section 8.3, Adverse Events, Serious Adverse Events, and Other Safety Reporting and Section 10.4, Appendix 4 Adverse Events: Definitions and Procedures for Recording, Evaluating, Follow-up, and Reporting.
 - Any serious clinically significant abnormalities (including those serious events persisting at the end of the study/early withdrawal) will be followed by the investigator until resolution or until a clinically stable endpoint is reached.
- Several safety measures are included in this protocol to minimize the potential risk to participants, including the following:
 - Sentinel participants will be evaluated for safety before extending enrollment in each cohort. The blinded 48-hour post-vaccination safety data in these sentinel participants will be reviewed by the principal investigator(s) (PIs) and sponsor's study responsible physician (SRP)/medical officer. Randomization of additional participants will be paused until this 48-hour sentinel safety evaluation is completed.

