6.8. Study Pausing Rules

If a study vaccination is considered to raise significant safety concerns (and a specific set of pausing criteria have been met), further vaccination of participants may be paused after medical review as described below. The concerned data will then be reviewed by the DRC, after which the DRC will recommend whether the pause can be lifted or not, or whether other steps are needed.

1. The occurrence of any of the following events may lead to a pause in further study vaccination. This list is only applicable for concerned AEs that occur up to 4 weeks after each vaccination and for concerned SAEs from the first vaccination throughout the study. Death of a participant, considered related to study vaccine or if the causal relationship to the study vaccine cannot be excluded; OR
Note: All cases of death will be sent for DRC information. Upon their review, DRC may then decide whether a study pause is required.
2. One or more participants experience an SAE, a Grade 4 (solicited or unsolicited) AE, or a persistent (upon repeat testing) Grade 4 laboratory abnormality that is determined to be related to study vaccine; OR
3. One or more participants experience anaphylaxis or generalized urticaria within 24 hours of vaccination, clearly not attributable to other causes than vaccination with study vaccine; OR
4. Three or more participants experience a Grade 3 unsolicited AE of the same type (as per medical judgment of the sponsor), that is determined to be related to study vaccine, that persists for 72 hours or longer; OR one participant from sentinel cohort experiences a Grade 3 unsolicited AE that is determined to be related to study vaccine; OR
5. Three or more participants experience a persistent (upon repeat testing) Grade 3 laboratory abnormality related to the same laboratory parameter and considered related to study vaccine; OR One participant from sentinel cohort experiences a persistent (upon retesting) Grade 3 laboratory abnormality that is determined to be related to study vaccine; OR
6. Three or more participants experience a Grade 3 solicited AE of the same type, determined to be related to study vaccine, and persisting as Grade 3 for longer than 3 consecutive days (ie,

the day of occurrence of the AE is counted as Day 1); OR one participant from sentinel cohort experiences a Grade 3 solicited systemic AE that is determined to be related to study vaccine.

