For number 2 and number 5: to assess abnormal laboratory values, the test must be repeated at least once, within 48 hours of the site becoming aware of the abnormal value.

For number 4, number 5 and number 6: after each DRC review of similar AEs, the Committee will indicate the conditions under which it requires further notification and review of the subsequent similar AEs.

To enable prompt response to a situation that could trigger pausing rules, the investigator should notify the sponsor's medical officer or designee (AND transmit SAE form [if applicable] in a secure manner electronically or by facsimile [fax] to the sponsor), immediately and no later than 24 hours after becoming aware of any related AE of Grade 3 or above AND update the eCRF with relevant information on the same day the AE information is collected. A thorough analysis of all Grade 3 (or above) cases will be carried out by the sponsor's medical officer or designee, irrespective of whether the criteria for pausing the study are met. Based on the pausing criteria, the sponsor's medical officer or designee then decides whether a study pause is warranted. All sites will be notified immediately in case of a study pause. The sponsor's medical officer or designee is responsible for the immediate notification of DRC members and coordination of a DRC meeting in case of a study pause.

Vaccinations for an individual participant may be suspended for safety concerns other than those described in the pausing criteria, at the discretion of the investigator if he/she feels the participant's safety may be threatened. The sponsor's medical officer or designee or the investigator(s) (upon consultation with the sponsor's medical officer or designee) may initiate DRC review for any single event or combination of multiple events which, in their professional opinion, could jeopardize the safety of the participants or the reliability of the data.

Vaccinations for the study may be suspended for safety concerns other than those described above, or before pausing rules are met, if, in the judgment of the DRC, participant safety may be threatened.

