All SAEs and AEs leading to discontinuation from further study vaccination (regardless of the causal relationship) are to be reported from the moment of first vaccination until completion of the participant's last study-related procedure, which may include contact for safety follow-up. The sponsor will evaluate any safety information that is spontaneously reported by an investigator beyond the time frame specified in the protocol.

AEs of Grade 3 or Above that are Related to Study Vaccine

All AEs of Grade 3 or above that are related to study vaccine must be reported to the appropriate sponsor contact person by study-site personnel immediately, but no later than 24 hours of their knowledge of the events. Relevant AE information should be updated in the eCRF on the same day when the AE information is collected (see Section 6.8 Study Pausing Rules).

Serious Adverse Events

All SAEs occurring during the study must be reported to the appropriate sponsor contact person by study-site personnel immediately, but no later than 24 hours of their knowledge of the event.

Information regarding SAEs will be transmitted to the sponsor using the Serious Adverse Event Form, which must be completed and signed by a physician from the study site, and transmitted to the sponsor immediately, but no later than 24 hours of their knowledge of the event. The initial and follow-up reports of an SAE should be transmitted in a secure manner electronically or by facsimile (fax). Telephone reporting should be the exception and the reporter should be asked to complete the appropriate form(s) first.

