An SAE based on ICH and European Union (EU) Guidelines on Pharmacovigilance for Medicinal Products for Human Use is any untoward medical occurrence that at any dose:

- Results in death
- Is life-threatening
(The participant was at risk of death at the time of the event. It does not refer to an event that hypothetically might have caused death if it were more severe.)
- Requires inpatient hospitalization or prolongation of existing hospitalization
- Results in persistent or significant disability/incapacity
- Is a congenital anomaly/birth defect
- Is a suspected transmission of any infectious agent via a medicinal product
- Is Medically Important*

*Medical and scientific judgment should be exercised in deciding whether expedited reporting is also appropriate in other situations, such as important medical events that may not be immediately life-threatening or result in death or hospitalization but may jeopardize the participant or may

require intervention to prevent one of the other outcomes listed in the definition above. These should usually be considered serious.

If a serious and unexpected AE occurs for which there is evidence suggesting a causal relationship between the study vaccine and the event (eg, death from anaphylaxis), the event must be reported as a serious and unexpected suspected adverse reaction even if it is a component of the study endpoint (eg, all-cause mortality).

Any ILI and complications related to ILIs fulfilling the criteria of an SAE will be reported as such during the entire study period from the first vaccination.

Unlisted (Unexpected) Adverse Event/Reference Safety Information

An AE is considered unlisted if the nature or severity is not consistent with the applicable product reference safety information. For INFLUENZA G1 mHA, the expectedness of an AE will be determined by whether or not it is listed in the IB.

ATTRIBUTION DEFINITIONS

Assessment of Causality

The causal relationship to study vaccine is determined by the investigator. The following selection should be used to assess all AEs.

Related

There is a reasonable causal relationship between study treatment administration and the AE.

Not Related

There is not a reasonable causal relationship between study treatment administration and the AE.

The term "reasonable causal relationship" means there is evidence to support a causal relationship.

By definition, all solicited AEs at the injection site will be considered related to the study vaccine administration.

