Nausea [#]	Minimal symptoms; causes minimal or no interference with work, school, or self-care activities	Notable symptoms; Requires modification in activity or use of medications; Does NOT result in loss of work, school, or cancellation of social activities	Incapacitating symptoms; Requires bed rest and/or results in loss of work, school, or cancellation of social activities	Hospitalization; Inability to perform basic self-care functions
Diarrhea [#]	2 – 3 loose stools or < 400 gms/24 hours	4 – 5 stools or 400 – 800 gms/24 hours	6 or more watery stools or > 800 gms/24 hours or oral rehydration necessary	Hospitalization; Hypotensive shock OR IV fluid replacement indicated
Headache [#]	Minimal symptoms; causes minimal or no interference with work, school, or self-care activities	Notable symptoms; Requires modification in activity or use of medications; Does NOT result in loss of work, school, or cancellation of social activities	Incapacitating symptoms; Requires bed rest and/or results in loss of work, school, or cancellation of social activities; Use of narcotic pain reliever	Hospitalization; Inability to perform basic self-care functions
Fatigue [#]	Minimal symptoms; causes minimal or no interference with work, school, or self-care activities	Notable symptoms; Requires modification in activity or use of medications; Does NOT result in loss of work, school, or cancellation of social activities	Incapacitating symptoms; Requires bed rest and/or results in loss of work, school, or cancellation of social activities; Use of narcotic pain reliever	Hospitalization; Inability to perform basic self-care functions
Myalgia [#]	Minimal symptoms; causes minimal or no interference with work, school, or self-care activities	Notable symptoms; Requires modification in activity or use of medications; Does NOT result in loss of work, school, or cancellation of social activities	Incapacitating symptoms; Requires bed rest and/or results in loss of work, school, or cancellation of social activities; Use of narcotic pain reliever	Hospitalization; Inability to perform basic self-care functions

[#] Revised by the sponsor.

Systemic Illness	Mild (Grade 1)	Moderate (Grade 2)	Severe (Grade 3)	Potentially Life Threatening (Grade 4)
Illness or clinical adverse event (as defined according to	No interference with activity	Some interference with activity not requiring medical intervention	Prevents daily activity and requires medical intervention	Hospitalization [#]

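### One mild case of generalized urticaria can meet pausing criterion 3, but the 24-hour site notice covers only SAEs and related events of Grade 3 or above

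*Protocol*

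**What the plan says.** Protocol 6.8 lists six pausing criteria. Criterion 3 is met when one or more participants "experience anaphylaxis or generalized urticaria within 24 hours of vaccination", provided the event is clearly not due to something other than the study vaccine. It sets no severity grade and no seriousness condition.

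The same section then gives sites a reporting duty whose stated purpose is a fast response to anything that could trigger a pausing rule. They must notify the sponsor's medical officer "immediately and no later than 24 hours after becoming aware of any related AE of Grade 3 or above" and update the eCRF on the day the information is collected. The medical officer's detailed case analysis is likewise limited to events of Grade 3 or above. Section 8.3.1 carries the same floor ("All AEs of Grade 3 or above that are related to study vaccine must be reported") and separately requires all SAEs to be reported within 24 hours.

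The medical officer decides, after medical review, whether a pause is warranted.

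**The concern.** The reporting duty is narrower than the rules it serves. A non-serious Grade 1 or 2 generalized urticaria within 24 hours of a dose meets criterion 3 on one case, yet neither the Grade 3 notice nor the SAE notice covers it. The person who decides on a pause may then hear of it only through routine data flow, while other participants are still being dosed.

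This is a first-in-human product, and Section 2.3.3 counts the pausing rules for all participants among the safety measures that make the benefit-risk balance acceptable. Outside the sentinels, criteria 4 to 6 need three cases; criterion 3 needs one. The protocol thus treats this signal as one to act on early, but gives its mildest form no deadline.

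**Working it through.** The plan has no figure of its own to reproduce here. The check sets each trigger against the timed notices, tests whether a case below Grade 3 is possible, and counts who is covered by a timed review.

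**1. Triggers against timed notices (Protocol 6.8 and 8.3.1)**

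| Criterion | Least severe event that meets it | 24-hour notice? |
|---|---|---|
| 1 | Death, relation to vaccine not excluded | Yes, as an SAE |
| 2 | Related SAE, Grade 4 AE or persistent Grade 4 laboratory value | Yes |
| 3, anaphylaxis | No grade stated | Normally yes, as an SAE |
| 3, generalized urticaria | No grade or seriousness stated | Only if Grade 3 or above, or an SAE |
| 4, 5, 6 | Related Grade 3 AE or laboratory value | Yes |

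The other timed reports (pregnancy, product quality complaints, overdose) do not concern urticaria.

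**2. Can generalized urticaria be below Grade 3?** Yes. It is not listed in the Appendix 5 table, so the general scale applies. In both Appendix 4 (10.4) and Appendix 5 (10.5), Grade 3 requires that usual activities are prevented and also that medical intervention is needed. Grade 2 in the systemic illness row of Appendix 5 reads "Some interference with activity not requiring medical intervention". Widespread hives that do not stop daily activity fit Grade 1 or 2. The investigator may still class the case as medically important; Appendix 4 says of such events, "These should usually be considered serious". That is a judgment, so a non-serious case remains possible.

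**3. Other routes for such a case**

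- Sentinel 48-hour review (2.3.3, 4.1): timed, reaches the study responsible physician/medical officer, any grade.
- Seven-day DRC review (4.1, 10.3): timed, sentinel and ramp-up subsets only.
- Site observation (1.3.1: "Participants will be closely observed for a minimum of 30 minutes post-vaccination"), a diary call that "should be made to all participants 3 to 5 days after Day 1 and Day 57 visits", and the Day 8 and Day 64 visits: these limit how long the site is unaware, but set no deadline for telling the sponsor. Urticaria is not a solicited event (8.2), so the diary does not ask about it.
- Routine eCRF completion, informing the DRC of AEs of concern (both 10.3), DRC review of events that meet a pausing rule (4.1), and investigator consultation with the medical officer (6.8): no time limit on any of them.

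**4. Coverage of the timed reviews.** Inputs are Table 1 and the staged enrollment in 4.1. The stages add up: 5 + 12 + 43 = 60 in Cohort 1, 5 + 10 + 95 = 110 in Cohort 2, 170 in total.

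| | Participants | Active participants | Active doses |
|---|---|---|---|
| Sentinel | 5 + 5 = 10 | 4 + 4 = 8 | 8 + 4 + 2 = 14 |
| Ramp-up | 12 + 10 = 22 | 10 + 8 = 18 | 20 + 8 + 4 = 32 |
| Both | 32 | 26 | 46 |
| All | 170 | 150 | 250 |
| Outside | 138 | 124 | 204 |

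Dose sums are in the order Groups 1 and 2 (two active doses), Groups 4 and 5 (two), Groups 6 and 7 (one active dose, then placebo):

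- Sentinel: 4×2, 2×2, 2×1.
- Ramp-up: 10×2, 4×2, 4×1.
- All: 100×2 for Groups 1, 2, 4 and 5, plus 50×1 for Groups 6 and 7, = 250.

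Shares of active doses: 14/250 = 5.6% have the 48-hour review, 46/250 = 18.4% have either review, and 204/250 = 81.6% have neither. Direct check of the last row: 36×2 + 44×2 + 44×1 = 204.

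**The case against.** The strongest reply is that very little is left uncovered. The event must be generalized urticaria within 24 hours, with no other clear cause, below Grade 3, not judged medically important, and outside the first 32 participants. An emergency room visit alone makes it Grade 4 under Appendix 4. Candidates with chronic urticaria or earlier serious vaccine reactions are excluded (5.2). Section 6.8 lets the investigator, in consultation with the medical officer, initiate DRC review of any single event, and 4.1 has the DRC look at blinded safety data regularly. For most participants the next scheduled contact after the observation period is the call at 3 to 5 days, so late detection may outweigh late notification. The intent of the notice is plain, and a sensible investigator would probably telephone anyway.

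Much of this stands. The case is narrow, the benefit of a fix is modest, and 81.6% measures review coverage rather than doses at risk. What does not stand is the claim that other routes close the gap: the consultation route is discretionary, and neither it nor the regular DRC review sets a reporting deadline for sites. Clear intent does not help when the operative sentence states a narrower scope.

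**Conclusion.** The concern holds. The 24-hour notice in 6.8 and 8.3.1 does not cover one event that can meet criterion 3: a non-serious generalized urticaria of Grade 1 or 2. Outside the sentinel and ramp-up reviews, which is 138 of 170 participants, 124 of 150 active participants and 204 of 250 active doses if every dose is given, nothing in the Protocol or SAP puts a time limit on telling the sponsor.

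The consequence is limited. Section 6.8 says vaccination may be paused after medical review, whereas 4.1 says it will be paused once a rule is met; on either reading the sponsor must first learn of the event. The first-dose gate from Cohort 1 to Cohort 2 is not materially affected, because the DRC reviews all AEs in the first 17 participants. The documents give no rate for this event, so neither its probability nor the number of participants dosed during a delay can be stated.

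The mismatch in wording is certain. Whether it persists in practice depends on the DRC charter, the DRC SAP and the eCRF guidelines, which were not available and could set a deadline.

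**What to change.** In 6.8 and 8.3.1, extend the 24-hour notification and same-day eCRF entry to any event that meets, or may meet, a Section 6.8 criterion. Name anaphylaxis and generalized urticaria within 24 hours of vaccination, regardless of grade. Widen the sentence in 6.8 on the medical officer's case analysis to match.

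The pausing criteria, sample size and analyses do not change. The cost is a sentence in each of two sections, brief site training and a few more expedited notices. The clock would still start when the site becomes aware, so the change does not shorten the time before a participant reports the event.
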